13.0 Vulnerable Populations

13.1 If the research involves individuals who are vulnerable to coercion or undue influence, please describe additional safeguards you will include to protect their rights and welfare. Consider the applicable items listed below:

- *If the research involves Virginia Tech students, indicate whether these are students of any of the investigators. If so, describe whether the activities will take place during class time as part of the curriculum and the steps you will take to reduce the possibility that students feel obliged to participate in order to improve their course grade. The HRPP can provide further guidance as needed. Describe whether you will request access to student records (e.g., SAT, GPA, GRE scores).*
- *If the research involves employees of Virginia Tech or the research sponsor, describe steps you will take to ensure that the employees are freely participating and describe how their data will be protected from inspection by their supervisors.*
- *If the research involves Virginia Tech NCAA athletes, you must obtain approval from the athletic department.*
- *For research involving Montgomery County Public Schools, you must obtain county approval (after obtaining contingent Virginia Tech approval). Other locales have different requirements; please check on these and describe here. Approval is typically granted by the superintendent, principal, and classroom teacher (in that order). Approval by an individual teacher is insufficient. School approval, in the form of a letter or a memorandum should be uploaded as a supporting document.*
- *If the research involves pregnant women, review “CHECKLIST: Pregnant Women (HRP-412)” to ensure that you have provided sufficient information in this protocol.*
- *If the research involves prisoners, review “CHECKLIST: Prisoners (HRP-415)” to ensure that you have provided sufficient information in this protocol.*
- *If the research involves persons who have not attained the legal age for consent to treatments or procedures involved in the research (minors), review the “CHECKLIST: Minors (HRP-416)” to ensure that you have provided sufficient information in this protocol.*
- *If the research involves cognitively impaired adults, review “CHECKLIST: Cognitively Impaired Adults (HRP-417)” to ensure that you have provided sufficient information in this protocol.*

21-1072 Validation and application of wearable sensors for capturing responses to losses of balance

Employees of Virginia Tech may be included. If so, it will be emphasized that their participation is entirely voluntary.

No other vulnerable populations listed above will be included.

14.0 Number of Subjects

14.1 Indicate the total number of subjects to be enrolled and how this number was determined (e.g., sample size calculation [show], number of available subjects in a finite pool, number of tests funding award would allow):

60 participants will be enrolled. This number is based upon a formal sample size analysis described here:

30 non-balance training participants will be recruited for our primary objective. Given that this objective is for validation, no formal effect sizes could be determined. Rather, we estimated 30 participants for this objective to be a reasonable number based upon our available resources and the number of expected LOBs estimated from prior work [Handelzalts et al. 2020].

30 balance training participants will be recruited for our secondary objective and be based upon Hypothesis 3: NT and TT participants will exhibit improved LOB responses after lab-induced trips and slips compared to ST participants.

The sample size was determined using data from lab-induced trips among community-dwelling older adults aged 65 years or older (Pavol et al., 2001). The effect size index (i.e., Cohen's $d = 1.45$) was determined using the difference in mean trunk angle from vertical at the time of recovery foot ground contact between fallers and non-fallers (17.4°) and the combined standard deviation (12°). The difference in means was considered the minimal clinically important difference based on the anchor-based method (Rai et al., 2015). Using G*Power (Faul et al., 2007) for an independent t-test with 80% power and a one-sided Type I error (or alpha) of 5%, a sample size of seven participants per group is needed. In an effort to be conservative and account for any participants withdrawing from the study, 10 participants per balance training group (TT,NT,ST) will be recruited.

Handelzalts, S., N.B. Alexander, N. Mastruserio, L.V. Nyquist, D.M. Strasburg, and L.V. Ojeda. Detection of Real-World Trips in At-Fall Risk Community Dwelling Older Adults Using Wearable Sensors. *Front Med*, 2020. 7: p. 514.

14.2 If this is a multi-site study, indicate the number of subjects to be enrolled at this site and the total to be enrolled from all sites:

21-1072 Validation and application of wearable sensors for capturing responses to losses of balance

Not a multi-site study.

14.3 If applicable, indicate the number of potential subjects you expect to screen for enrollment, and the number of subjects you will need to complete the research procedures:

N/A

14.4 If the study has more than one procedure, indicate the total number of subjects to undergo each procedure separately:

30 participants will be assigned to be non-balance training participants

30 participants will be assigned to be balance training participants, with 10 completing each of the three types of training under investigation (TT, NT, ST).

Other than these differences in balance training, all other testing will be the same for all participants.

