2.0 Objectives

2.1 Describe the purpose, specific aims, or objectives of this study:

The primary objective is to validate the use of wearable sensors for capturing responses to losses of balance (LOBs). During laboratory testing, we will use wearable sensors and a laboratory-based optoelectronic motion capture system to simultaneously measure responses to LOBs after laboratory-induced trips and slips. During real-world testing, we will use wearable sensors to measure responses to LOBs after any naturally-occurring trips or slips during the real-world daily lives of participants.

The secondary objective of this study is to compare the effects of three balance training exercises on responses to LOBs measured in the laboratory and in the real-world during daily life.

2.2 State the hypotheses to be tested:

Hypotheses for our primary objective that will involve non-balance training participants:

Hypothesis 1: LOB response measures obtained from the wearable sensors after lab-induced trips and slips will exhibit statistical agreement with the same measures obtained simultaneously from a laboratory-based optoelectronic motion capture system.

Hypothesis 2: Real-world LOB responses will show greater variety than laboratory-induced LOB responses.

Hypotheses for our secondary objective that will involve balance training participants:

Hypothesis 3: NT and TT participants will exhibit improved LOB responses after lab-induced trips and slips compared to ST participants.

Hypothesis 4: NT and TT participants will exhibit statistically-equivalent LOB responses after lab-induced trips and slips.

Hypothesis 5: NT and TT participants will exhibit improved LOB responses after any naturally-occurring real-world trips and slips.

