To address Hypothesis 2, a repeated-measures ANOVA (with a random effect for subject) will first be used to compare means of key kinematic measures of LOB responses between environments (real-world vs lab). Second, we will compare statistical variability by examining the model residuals between real-world and lab environments using hypothesis testing (essentially Levene's test) and interval estimation to quantify potential differences in variability.

Hypothesis 3: NT and TT participants will exhibit improved LOB responses after lab-induced trips and slips compared to ST participants.

To address Hypothesis 3, response variables will be compared between NT, TT, and ST participants using a one-way ANOVA with group as the independent variable and covariates included as needed. A significant effect of group will be followed by post-hoc analysis using Dunnett's test to determine whether NT, TT, or both differ from ST.

Hypothesis 4: NT and TT participants will exhibit statistically-equivalent LOB responses after lab-induced trips and slips.

To address Hypothesis 4, agreement of response variables between NT and TT participants will be evaluated using statistical equivalence test.

A comparison between the three balance training exercises on LOB responses after any naturally-occurring real-world trips will be done qualitatively and thus not have an explicit hypotheses to be tested.

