16.0 Withdrawal of Subjects

16.1 Describe circumstances under which you anticipate subjects could be withdrawn from the research without their consent:

Participants can be withdrawn if they fail to follow the investigator instructions during sessions or miss scheduled sessions.

16.2 If applicable, describe any procedures for orderly termination (e.g., discontinuation of a study drug or debriefing after a behavioral intervention):

N/A

16.3 Describe procedures that you will follow when subjects withdraw from the research, including partial withdrawal from procedures with continued data collection (e.g., participant declines to continue with regular blood draws, but continues with periodic behavioral questionnaires):

All sessions and data collections will be terminated when a participant withdraws from the study. Partial withdraw will not be accommodated, meaning that participants cannot withdraw from some of the procedures but remain involved in others.

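### Seven per group gives 80% power for a single one-sided t-test, but only 48–73% for the ANOVA-then-Dunnett procedure planned for Hypothesis 3

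*Combined protocol and SAP*

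**What the plan says.** Section 14.1 bases the 30 balance training participants on Hypothesis 3. It takes a trunk-angle difference of 17.4° and a standard deviation of 12°, hence d = 1.45, and continues: "for an independent t-test with 80% power and a one-sided Type I error (or alpha) of 5%, a sample size of seven participants" per group. It then adds a margin: "In an effort to be conservative and account for any participants withdrawing from the study, 10 participants per balance training group" are recruited.

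Section 5.2 gives the analysis of the same hypothesis as a one-way ANOVA on three groups, "with group as the independent variable and covariates included as needed". It goes on: "A significant effect of group will be followed by post-hoc analysis using" Dunnett's test, "to determine whether NT, TT, or both differ from ST".

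Section 2.2 words Hypothesis 3 directionally: "NT and TT participants will exhibit improved LOB responses after lab-induced trips and slips compared to ST participants". Hypothesis 4 expects the two perturbation arms to be alike: "NT and TT participants will exhibit statistically-equivalent LOB responses after lab-induced trips and slips".

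Section 16.3 says of withdrawals: "All sessions and data collections will be terminated when a participant withdraws from the study". Partial withdrawal is not accommodated.

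**The concern.** The test used for sizing is not the test that will be run. The t-test makes one comparison between two groups. The planned procedure requires a three-group F test to be significant first, and then judges two comparisons at Dunnett-adjusted critical values. Both steps cost power, and the protocol gives no power for the combination.

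Section 5.2 also leaves three choices open: the ANOVA level, whether Dunnett's test is one- or two-sided (14.1 is one-sided; 5.2 speaks only of a difference), and whether success means each comparison on its own, at least one, or both.

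What is at stake is the withdrawal margin. Seven is the only number the protocol calls sufficient, so 10 reads as allowing three losses per group. The laboratory session follows three weeks of training, so a participant who withdraws during training gives no Hypothesis 3 outcome.

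**Working it through.** **Inputs.** From 14.1: difference 17.4°, SD 12°, one-sided 5%, 80% power, seven per group needed, 10 recruited. From 5.2: three-group ANOVA, then Dunnett against ST. Assumed, because the documents do not say: ANOVA at 5%, Dunnett family-wise 5%, equal variances, no covariates, and NT and TT both at d = 1.45 from ST (Hypothesis 4 expects equal effects; 14.1 does not state it).

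**Step 1: the protocol's own figure.** d = 17.4/12 = 1.45. For a two-sample t-test the noncentrality is d√(n/2) on 2n − 2 degrees of freedom. At n = 7 this is 1.45 × √3.5 = 2.71, the one-sided 5% critical value on 12 df is 1.782, and power is 81.9%. At n = 6 it is 75.5%, and at n = 10 it is 92.9%. Seven is therefore the smallest n that reaches 80%, as stated.

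**Step 2: the ANOVA gate.** With means 0, 1.45 and 1.45 in SD units, the noncentrality is λ = n × (2/3) × 1.45² = 1.4017n, on 2 and 3(n − 1) df. At n = 7, λ = 9.81, the critical F(2, 18) is 3.555, and power is 73.3%. At n = 8, 9 and 10 it is 80.2%, 85.6% and 89.6%. No comparison counts unless the gate passes, so under these assumptions 73.3% is a ceiling at seven per group.

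**Step 3: the gated procedure.** Each comparison uses t = (arm mean − ST mean)/(s√(2/n)) on 3(n − 1) df. The Dunnett critical values at n = 7 are 2.040 one-sided and 2.399 two-sided; at n = 10 they are 1.997 and 2.333. Power (%), from 2,000,000 simulated trials per cell:

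| n per group | One-sided: each | One-sided: at least one | One-sided: both | Two-sided: each | Two-sided: at least one | Two-sided: both |
|---|---|---|---|---|---|---|
| 7 | 66.8 | 73.3 | 60.4 | 60.6 | 73.0 | 48.2 |
| 8 | 74.3 | 80.2 | 68.4 | 68.3 | 79.9 | 56.6 |
| 9 | 80.4 | 85.6 | 75.2 | 74.8 | 85.4 | 64.3 |
| 10 | 85.2 | 89.6 | 80.8 | 80.2 | 89.5 | 71.0 |

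Two-sided power for both comparisons first reaches 80% at 12 per group (81.5%).

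**Step 4: the withdrawal margin.** Starting from 10, the loss per group that still leaves 80% is:
- one, for one-sided each;
- none, for two-sided each or one-sided both;
- two, for one-sided at least one;
- one, for two-sided at least one (two is borderline, at 79.9%);
- already short at 10, for two-sided both.

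**Step 5: sensitivity.** If one arm has half the effect (d = 0.725), λ = n × 1.45²/2, and the gate passes 60.0% at n = 7 and 78.9% at n = 10. The full-effect arm then has 78.5% one-sided and 77.3% two-sided at n = 10; 11 per group gives 82.9% and 81.9%. With a 10% gate, equal effects and n = 7, the results for each/at least one/both are 73.1/83.8/62.3% one-sided and 62.7/77.2/48.2% two-sided. Only one-sided at least one then reaches 80%.

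**The case against.** The strongest reply is that the trial recruits 10 per group, not seven, and section 14.4 plans for 10 to complete each type of training. At 10, five of the six readings in the table reach 80%, and the documents forecast no attrition rate. That is true, and it is why the point does not threaten the design. It does not rescue the statement that seven is enough, nor the margin built on it.

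The 48% end comes from the strictest reading: two-sided, both comparisons required. Section 5.2 does not demand both, and the one-sided alpha in 14.1 and the directional hypothesis favour one-sided tests. On the one-sided, each-comparison reading the figures are 67% at seven and 85% at 10. The shortfall at seven remains.

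Covariates could recover power. If one covariate correlated 0.5 with the outcome, the gate at seven would pass about 85% of the time and each one-sided comparison would have about 80%; at a correlation of 0.3 these are 77% and 71%. The protocol names no covariate and no correlation, so its 80% cannot rest on this. The 73% ceiling does, however, hold only without covariates.

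The margins also assume equal losses. With eight in ST and 10 in each other arm, power per one-sided comparison is 79.4%; with 10 in ST and eight in each other arm, it is about 80%.

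Finally, Hypothesis 3 serves a secondary objective, and sizing on a simple contrast with some added margin is common practice. This limits the severity, but does not make the two sections agree.

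**Conclusion.** The concern holds. The 80% in 14.1 belongs to a test that 5.2 does not use. For the planned procedure, seven per group gives 48–73%, below 80% on every reading of sidedness and success. Ten per group gives 71–90%, and only the two-sided, both-comparisons reading falls short.

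These figures rest on a 5% gate, equal variances, no covariates and equal effects of d = 1.45 in NT and TT. A looser gate or a strong covariate would raise them; an intermediate effect in one arm would lower them. The sample-size justification and the implied withdrawal margin should be corrected. The number recruited can stand in the base case.

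**What to change.** Make 5.2 and 14.1 describe the same test.

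In 5.2, add: *ANOVA at 5%; Dunnett contrasts NT vs ST and TT vs ST, one-sided, family-wise 5%; each contrast is judged separately.* One-sided testing matches the direction of Hypothesis 3 and the alpha already in 14.1.

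In 14.1, keep the sentences that derive d from trunk angle, and replace the t-test power sentence and the withdrawal sentence with: *Assuming NT and TT each differ from ST by d = 1.45 and no covariates, with 10 completers per group this procedure has about 85% power per comparison and 81% for both; 80% per comparison holds down to nine in each group. If one arm has half that effect, power for the full-effect arm is about 78% at 10 per group.*

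If two-sided tests are preferred, the figures at 10 per group are 80% per comparison, 71% for both, and 77% for the full-effect arm.

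An optional alternative is to drop the ANOVA gate and go straight to the one-sided Dunnett contrasts, which control the family-wise error by themselves. At n = 7/8/9/10, power is then 75/81/85/89% per comparison and 62/70/76/82% for both, and a weaker second arm does not reduce the per-comparison figure.

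The cost is wording in two sections, with no extra participants in the base case. The downsides are a smaller stated power and margin, one-sided contrasts that cannot declare ST better, and, if the gate is kept, about 78% power when one arm has half the effect.

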Each ST session will involve general balance and strength exercises adapted from the Otago Exercise Program (Campbell et al., 1997). Otago has shown its effectiveness in reducing fall risk in community-dwelling older adults, and thus it is chosen among many other general exercise interventions to increase the level of evidence for demonstrating efficacy. In addition, similar to NT or TT, it can be performed individually. Each ST session will involve strength and balance exercises with varying ankle weights or difficulty of the balance exercises (e.g., holding onto a wall or no support), which will be progressively increased based upon the performance of participants. Strength exercises will include controlled squatting, lunges, knee bends, hip extensions, leg side raises, and toe raises. Resistance will be provided with ankle weights. Balance exercises will involve standing with feet side-by-side at decreasing distance, standing with one foot in front of the other, and standing on one foot. Difficulty will progress by increasing angle weights and increasing difficulty of standing position (e.g. feet side by side and moving them closer together, one foot in front of the other and increasing the distance between them, and asking subjects to move their body while in these challenging feet positions). The progression of difficulty will be based on the investigators perception of the improving ability of the participant.

Campbell, A. J., Robertson, M. C., Gardner, M. M., Norton, R. N., Tilyard, M. W., & Buchner, D. M. (1997). Randomised controlled trial of a general practice programme of home based exercise to prevent falls in elderly women. *BMJ*, 315(7115), 1065-1069.

7.2 List the name of all drugs (including any vitamins, supplements, herbs, or nicotine) to be used in the study. Indicate whether they have FDA approval, and list any limitations for their use:

N/A

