- If the participant passes the health questionnaire, then a DEXA assessment for osteoporosis will take place. This assessment will be based upon a DEXA scan performed for this study, or DEXA scan completed within the last year.
- If a DEXA scan is performed for this study, the scan will take place in the Human Integrative Physiology Lab, led by [name]. [name] does not have a role in the current work, but his lab will be providing this service to the PI for a fee. The Human Integrative Physiology Lab is in the Garvin Innovation Building in the CRC ([name]). A member from the research team involved in this IRB application will meet the subject at this location to provide a lead. Trained staff in this lab will conduct the scan.
- If the participant passes the DEXA scan, she/he will have completed our screening process.
- A copy of the informed consent form will be delivered to the participant, and the first visit will be scheduled (at least 24 hours after delivery of the informed consent form).
- The investigator will meet the participant in our research lab. The investigator will confirm the inclusion criteria and ask if they have any questions about the informed consent form. All questions will be answered. If the participant still wants to participate, they will sign the informed consent form, and be provided a copy for them to keep.

Group Assignment and Training

- Participants will be randomly assigned to be either a non-balance training participant or a balance-training participant. Balance training participants will then be assigned to either TT, NT, or ST.
- If the participant is assigned to balance training, this training will be completed twice a week for three weeks. Each training session will be approximately 45 minutes in duration. The details of each type of training is described in detail in section 7.1.
- NT, TT, and ST will all be customized to participants' capabilities, and training difficulty will progressively increased based on participants' capabilities. For NT, difficulty will be increased by 1) adding the obstacle to training during all four phases, 2) leaning the participant farther forward during Phase 3, and asking subjects to walk faster during Phase 4. For TT, difficulty will be increased by increasing the maximum speed of the treadmill perturbations. For ST, difficulty will be increased by using heavier ankle

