21-1072 Validation and application of wearable sensors for capturing responses to losses of balance

weights and using more challenging balance postures. The progression of difficulty will be based on the investigators perception of the improving ability of the participant.

- If the participant is assigned no training, then no such training will be performed.
- All participants will then complete the two types of LOB response measurements described below.

Measure LOB responses in the laboratory:

- Each participant will complete a lab session to assess their response to an LOB after lab-induced trips and slips. This session will take place in our research lab on the VT campus ([name]). During these sessions, participants will wear a safety harness supported overhead to prevent impact with the floor in the event of an unsuccessful balance recovery. First, the appropriate size will be selected from a range of sizes we have in the lab. Second, the investigator will assist the participant in donning the harness, securing all straps and connections, and inspecting and confirming the overall fit. The PI ([name]) has extensive experience with the harnesses, and will train the student investigators in their use.
- Participants will also wear reflective markers so researchers can measure their movements with a laboratory motion capture system. As we have done for years, these markers will be affixed to clothing and skin at selected anatomical landmarks using double-sided tape. [name] will place markers on participants. Markers will be placed bilaterally on the shoes at the toes and heels, ankles, knees, hips, shoulders, elbows, wrists, and on a headband worn around the head.

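### No comparison of trained with untrained participants is planned, so Hypotheses 3 and 4 cannot show whether any of the trainings improves laboratory balance responses

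*Combined protocol and SAP*

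**What the plan says.** **Allocation.** Section 8.2 (Group Assignment and Training) states: "Participants will be randomly assigned to be either a non-balance training participant or a balance-training participant". It continues: "Balance training participants will then be assigned to either TT, NT, or ST", without repeating that this second step is random. Section 14.4 gives the sizes: "30 participants will be assigned to be non-balance training participants", and 10 for each type of training.

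**Testing.** Section 8.2 says "Each participant will complete a lab session to assess their response to an LOB after lab-induced trips and slips". Section 14.4 adds: "Other than these differences in balance training, all other testing will be the same for all participants".

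**Analysis.** For Hypothesis 3, section 5.2 says that "response variables will be compared between NT, TT, and ST participants" by one-way ANOVA, followed by Dunnett's test with ST as reference. Hypothesis 4 is an equivalence test of NT against TT. No section plans a comparison of laboratory responses between trained and untrained participants. Section 14.1 ties the 30 untrained participants to the validation objective.

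**Comparator and design.** ST is adapted from the Otago programme, of which section 7.1 says "Otago has shown its effectiveness in reducing fall risk in community-dwelling older adults". Section 5.1 describes the training comparison as posttest-only, so no within-person change is available.

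**The concern.** With an active reference arm and no measurement before training, the planned contrasts are all relative to another training. If NT and TT do not differ from ST, the data are compatible with all three trainings helping and with none helping. If NT and TT are declared equivalent, both may be effective or both ineffective.

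The question lies within the study's stated interests. Section 3.3 presents the study as measuring what the non-treadmill training does to responses after laboratory-induced and natural trips and slips. Section 18.1 notes that the benefit of the training has not yet been formally evaluated. On the text of section 8.2, the trial will hold data from a concurrently randomised untrained group, three times the size of each training arm and tested in the same laboratory session. The plan does not use those data for this purpose.

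**Working it through.** **Inputs.** Difference 17.4° and SD 12° in trunk angle, one-sided alpha 5%, power 80%, 7 needed and 10 recruited per arm (14.1); 30 untrained (14.4). Assumptions of this check: the SD of 12° holds in all four groups, there are no losses, and Dunnett tests are two-sided at 5%, because section 5.2 states no direction for the post-hoc test.

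**1. The plan's own figure.** d = 17.4/12 = 1.45. Exact noncentral-t power for a one-sided two-sample t-test is 75.5% with 6 per group and 81.9% with 7. The stated 7 per group is reproduced.

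**2. Formulas.** For groups of n1 and n2:
- SE = 12 × √(1/n1 + 1/n2)
- simultaneous half-width = c × SE, where c is the Dunnett critical value (found by simulation)
- power per contrast = 1 − F(c), where F is the noncentral t distribution function with the residual df and noncentrality d/√(1/n1 + 1/n2)

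**3. Results.** Residual df are 30 − 3 = 27 for three groups and 60 − 4 = 56 for four.

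| Contrast | SE | df | c | Half-width | Power, d = 1.45 | Power, d = 1.0 | Detectable at 80% |
|---|---|---|---|---|---|---|---|
| NT or TT v ST, as planned | 12 × √(1/10 + 1/10) = 5.37° | 27 | 2.33 | 12.5° | 81% | 47% | 17.1° |
| NT or TT v ST, four-group error term | 5.37° | 56 | 2.27 | 12.2° | 83% | 49% | 16.7° |
| NT, TT or ST v untrained (three contrasts) | 12 × √(1/10 + 1/30) = 4.38° | 56 | 2.45 | 10.7° | 93% | 62% | 14.5° |

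The SE against untrained is 1 − 4.38/5.37 = 18% smaller than against ST.

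**4. What an active comparator does.** Suppose, for illustration only, that NT improves on no training by d = 1.45 and ST by half of that, 0.725. The NT–ST difference is then 1.45 − 0.725 = 0.725, and the planned Dunnett contrast has 26% power. The NT–untrained contrast has 93%. The planned analysis would then probably show no difference although both trainings work, and nothing in it would reveal this.

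**5. Comparability of the untrained group.** The sections do not agree on when the untrained participants have their lab session.
- Sections 5.1 and 8.1 place it after three weeks of sensor wear. Both cohorts then reach the lab about three weeks into the study.
- The measurement steps in section 8.2 list the lab session first and sensor wear over the following weeks. Section 6.1 has participants trained on the sensors during the lab session, which fits that order. Untrained participants would then be tested before any such interval, and trained participants after three weeks of training.

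Section 14.1 also speaks of recruiting each cohort for its own objective, which sits uneasily with the random split in section 8.2.

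**The case against.** The strongest reply is that the protocol describes two sub-studies: a one-group validation study and a three-arm training comparison (2.2, 5.1, 14.1). Hypothesis 3 asks whether NT and TT beat ST, and the planned ANOVA with Dunnett's test answers that. No hypothesis about laboratory responses claims that training beats no training. This stands: the proposal adds a secondary question and does not repair a faulty test. It explains why the contrast is absent, but it is no reason to leave it out, because using the same laboratory data twice does not harm the validation.

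A reader might infer more than the documents support in four ways.
- **That a null result against ST is uninterpretable.** It would still mean that superiority over ST was not shown. What it leaves open is whether training has any effect. Section 7.1 calls Otago effective for fall risk, not for movement responses to induced trips, so whether ST acts on this outcome is itself unknown.
- **That Hypothesis 3 loses material precision.** The SE against ST is 5.37° either way. The four-group error term gains about 2 points of power and 0.3° of half-width, and it assumes equal variance in a group that supplies 29 of the 56 df.
- **That the untrained group settles the question.** Trained participants have six one-on-one sessions (two a week for three weeks, 7.1) that untrained participants do not. A difference from untrained therefore mixes training with contact and familiarity. ST shares the session schedule, so it remains the better control for those.
- **That the data already exist.** The protocol is prospective; it shows only that the data would be collected in any case.

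**Conclusion.** The point holds as a limit on what the trial can conclude, not as a fault in the Hypothesis 3 test. As planned, the trial can say whether NT or TT beats ST and whether NT and TT are equivalent. It cannot say whether any of them improves laboratory responses over no training. Contrasts with the untrained group would estimate this with a simultaneous half-width of 10.7° and 93% power at the planning effect. At d = 1.0 the power is 62%, so a null against untrained would not be conclusive either.

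These figures rest on a common SD of 12°, full groups of 10 and 30, and a separate 5% level for the secondary family. If all five contrasts (two against ST, three against untrained) shared one 5% level by Bonferroni, power at d = 1.45 and d = 1.0 would be 90% and 53% against untrained, and 72% and 34% against ST. The causal reading rests on allocation being random as section 8.2 states, and on the timing of the lab session being comparable.

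**What to change.** In section 5.2:
1. Keep the three-group ANOVA and the Dunnett test against ST as the Hypothesis 3 analysis. A four-group error term for these contrasts is optional, since it gains little and assumes equal variance.
2. Add, as a separate secondary family, contrasts of NT, TT and ST against the untrained group, with Dunnett-type simultaneous confidence intervals for three comparisons. State that this family has its own 5% level and does not alter the Hypothesis 3 test. An unequal-variance version can serve as a sensitivity analysis.
3. State that these contrasts include the effect of six sessions of contact and familiarity as well as training.

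Elsewhere:
4. Reconcile sections 5.1 and 8.1 with 6.1 and the measurement steps in 8.2 on the order of lab session and sensor wear for untrained participants, and state any remaining difference in timing from the trained arms.
5. Confirm that allocation to trained or untrained is random as in 8.2, given the recruitment by objective in 14.1, and state whether assignment to TT, NT and ST is random too.

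The cost is wording: no extra participants, visits or measurements. The amendment should be made before laboratory outcomes are compared between groups, or the contrasts cannot be called pre-specified.
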